7.2.2.3 Brief Pain Inventory-Short Form

The full BPI-SF questionnaire will be completed by the subject at the randomization visit and at each subsequent site visit until the Month 6 visit (Month 6 PTOp visit if subject is in the PTOp). The questionnaire will be administered in an electronic format using the eDiary [see Section 7.2.2.1].

The BPI-SF is a validated, self-administered questionnaire, developed to assess the severity and impact of pain. The BPI-SF provides a direct and comprehensive means of measuring pain intensity, location of pain, and the extent to which pain interferes with the subject's

daily activities. The BPI was originally designed to assess pain in cancer subjects but has proven to work in other painful conditions including neuropathic pain and FD [Cleeland 2002].

The BPI-SF allows subjects to rate the severity of their pain (4 questions assessed on an NRS-11) and the degree to which their pain interferes with common dimensions of feeling and function (7 questions assessed on an NRS-11). Location of pain is also indicated on a body scheme by the subject.

A sample of the BPI-SF (in English) is provided in [Appendix 3](#).

The sponsor has been granted a license agreement for the use of the BPI-SF.

7.2.2.4 Patient Global Impression of Severity

Two PGIS questionnaires will be completed by the subject at the randomization visit and at each subsequent site visit until the Month 6 visit (Month 6 PTOP visit if subject is in the PTOP): a PGIS-D and a PGIS-P. The questionnaires will be administered in an electronic format using the eDiary.

The PGIS questionnaires are self-administered 1-item questionnaire designed to assess subject's impression of disease severity (PGIS-D) and neuropathic pain severity (PGIS-P). Subjects will rate the overall severity of the disease and neuropathic pain symptoms over the past 7 days on a 4-point scale (1–4) scored as: “none”, “mild”, “moderate”, or “severe”.

Samples of the PGIS-D and PGIS-P questionnaires are provided in [Appendix 4](#).

7.2.2.5 Patient Global Impression of Change

Two PGIC questionnaires will be completed by the subject starting at Month 1, and at each subsequent site visit until the Month 6 visit (Month 6 PTOP visit if subject is in the PTOP): a PGIC-DS and a PGIC-PS. The questionnaires will be administered in an electronic format using the eDiary.

The PGIC questionnaires are self-administered 1-item questionnaires designed to assess subject's impression of change since study treatment start in disease severity (PGIC-DS) and neuropathic pain severity (PGIC-PS). Subjects will rate their change since they started study treatment in the overall severity of the disease symptoms (PGIC-DS) and change in the overall severity of neuropathic pain (PGIC-PS) on 7-point scales (1 to 7) scored as: “very much improved,” “much improved,” “minimally improved,” “no change,” “minimally worse,” “much worse,” or “very much worse”.

Samples of the PGIC-DS and PGIC-PS questionnaires are provided in [Appendix 4](#).

7.2.2.6 Center for Epidemiologic Studies Depression Scale Revised

The CESD-R-20 will be completed by the subject at the randomization visit and Month 6 (Month 6 PTOF visit if subject is in the PTOF). The questionnaire will be administered in an electronic format using the eDiary.

The CESD was created in 1977 [Radloff 1977] and revised in 2004 (CESD-R-20 [Eaton 2004]). This self-report scale is well known and remains one of the most widely used instruments in the field of psychiatric epidemiology.

The 20 items in the CESD-R-20 scale measure symptoms of depression in nine different groups as defined by the American Psychiatric Association Diagnostic and Statistical Manual, fifth edition.

The total CESD-R-20 score is calculated as a sum of responses to all 20 questions. A score equal to or above 16 indicates a person at risk of clinical depression.

A sample of the CESD-R-20 (in English) is provided in [Appendix 5](#).

The use of the CESD-R-20 is not covered by a license.

7.2.2.7 Echocardiography

A central echocardiography vendor (see echocardiography manual for contact details) will be used for all protocol-mandated echocardiographies, including re-tests, and echocardiographies performed at unscheduled visits.

A re-test may be performed if the result for an echocardiography is missing (e.g., unreadable echocardiography) or to repeat an abnormal echocardiography. A re-test does not need to be reported as an unscheduled visit [see Section 7.1.2].

Standard 2D/Doppler echocardiographies will be collected at the randomization visit, and Month 6 (Month 6 PTOF visit if subject is in the PTOF). Echocardiographies will be acquired by trained sonographers/technicians using the echocardiography Image Acquisition Guidelines. The sonographers/technicians will have to be qualified by the central echocardiography vendor prior to any acquisition of echocardiographies in a study subject. Whenever possible, the same sonographer/technician should acquire all echocardiographies performed in one subject. The site personnel will electronically transmit the echocardiographies to the central echocardiography vendor for central reading.

The overview of the assessment criteria and read procedures used by the echocardiography vendor will be described in a charter.

Central echocardiography reports will be provided by the central echocardiography vendor to the investigator/delegate. In the event of specific echocardiography abnormalities, the central echocardiography vendor will alert the sponsor and the site personnel. All

echocardiography reports must be reviewed, signed, and dated by the investigator/delegate within 10 working days of receipt and filed with the source documentation.

Incidental clinically relevant findings on echocardiographies will be reported in the Medical History or as an AE in the eCRF, as applicable.

The measures/assessments evaluated by the central echocardiography vendor include but are not limited to:

- LVMI for height^{2.7} (g/m^{2.7});
- Posterior wall thickness (mm);
- Left ventricular mean wall thickness (mm);
- LVEF (%);
- Left ventricular end diastolic volume (mL);
- Left ventricular end systolic volume (mL);
- Left atrial volume (mL).

Details on echocardiography procedures (recording, transfer of data and reporting) will be provided in the echocardiography manual.

7.2.2.8 Exit interview (US and Canada)

English-speaking subjects in US and Canada will be contacted by an external CRO to set an interview as soon as possible after the end of study treatment phase or EOT visit, ideally within 2 weeks. The interviews will be conducted via telephone by qualified staff from the CRO following the semi-structured interview guide (“Discussion Guide for the Exit Interview”). The interviews will take approximately 45 minutes and will be audio-recorded and then transcribed; the audio files and transcripts will be de-identified and securely transferred to the sponsor by the CRO.

The purpose of exit interviews is to further explore what constitutes meaningful changes on the neuropathic pain (assess with modified BPI-SF3) and GI symptom (diarrhea and abdominal pain) questions from a subject’s perspective. Subjects will also be asked about meaningful change on the PGIC and PGIS questions.

Further details are provided in the separate documents “Exit interview sub-study protocol” and “Discussion Guide for the Exit Interview”. After the first 5 interviews are completed, the CRO staff will meet with the sponsor to review the de-identified data, discuss the findings at that stage, and adjust the interview process, if needed.

The interviews will be analyzed and interpreted by the CRO and reported in a separate report.

7.2.3 Safety assessments

The definitions, reporting and follow-up of AEs/SAEs and pregnancies are described in Section 9.

Unless otherwise specified, the date of each safety assessment will be collected in the eCRF.

7.2.3.1 Physical examination

Physical examination at screening includes the examination of the general appearance (heart, lungs, abdomen, skin, extremities, eyes, ears, nose, throat, lymph nodes, nervous system, etc.). At subsequent visits, physical examination includes, as a minimum, the examination of skin, heart, lungs, eyes, and ears.

Each physical examination must include a complete skin examination performed by the investigator/delegate. In the event of findings other than regular skin findings relevant to FD (e.g., angiokeratoma, hyperkeratosis), a dermatologist will conduct further examination per local standard practice, including performing skin biopsies if required to rule out or confirm a diagnosis.

Other examinations will be performed if indicated, based on medical history and/or symptoms.

Information for all physical examinations must be included in the source documentation at the study site.

The physical examination will be reported in the eCRF as either normal or abnormal; in the latter case, the investigator should specify whether it is clinically relevant. Clinically relevant physical abnormalities present at the time of signing of the ICF must be reported on the medical history or Fabry disease forms of the eCRF. Physical examination findings, which meet the definition of an AE [Section 9.1.1] and are made after signing of the ICF, must be recorded on the AE form of the eCRF.

7.2.3.2 Vital signs

HR, SBP, and DBP will be measured at each visit in a supine or sitting position and recorded in the eCRF. It is recommended to allow the subject to rest for at least 5 minutes, and to use the same arm and position (supine or sitting) throughout the study for an individual subject.

The date and exact actual clock time of vital sign assessments will be entered in the eCRF.

7.2.3.3 Weight and height

Height will be measured without shoes at screening.

Body weight will be measured in indoor clothing but without shoes at screening and each visit thereafter.

Body weight and height data will be recorded in the eCRF.

7.2.3.4 *Electrocardiogram assessment*

A standard pre-dose 12-lead ECG will be performed at all scheduled visits. At the Month 1 visit, 2 additional 12-lead ECGs will be performed 2 h and 4 h after study treatment administration.

A re-test may be performed if the result for an ECG is missing or to repeat an abnormal ECG. A re-test does not need to be reported as an unscheduled visit [see Section 7.1.2].

ECGs will be performed with the subject in a fully rested supine position after the subject has been allowed to rest for a minimum of 5 minutes prior to the measurement. The date and exact clock time of ECGs will be entered in the eCRF.

A central ECG vendor (see ECG manual for contact details) will be used for the evaluation of all protocol-mandated ECGs, including re-tests due to ECG abnormalities and ECGs performed at unscheduled visits. The site personnel will electronically transmit the ECGs to the central ECG vendor for central reading.

The following variables will be evaluated by the central ECG vendor: HR (bpm), PR (ms), QRS (ms), QT (ms), QTc according to Bazett's formula (QTcB) (ms), QTcF (ms) and any ECG findings. QTc (ms) will be calculated according to Bazett's and Fridericia's formula ($QTcB = QT/[RR]^{1/2}$ and $QTcF = QT/[RR]^{1/3}$, respectively).

ECG reports will be provided by the central ECG vendor to the investigator/delegate. If specific (pre-defined in the ECG manual) ECG abnormalities are observed, the central ECG vendor will alert the sponsor and the site personnel.

All ECG reports must be reviewed, signed and dated by the investigator or delegate within 10 working days of receipt and filed with the source documentation. The investigator/delegate must indicate on the ECG report whether abnormal values or findings are considered clinically relevant or not. Clinically relevant ECG findings that are known at the time of signing of the ICF must be recorded in the medical history or FD forms of the eCRF. Any clinically relevant ECG abnormalities detected after signing of the ICF must be reported as an AE or SAE as appropriate [see Section 9], and must be followed until the finding returns to normal, is considered stable, or until the change is no longer clinically relevant.

Details on ECG procedures (recording, transfer of data and reporting) will be provided in the ECG manual.

7.2.4 Laboratory assessments

7.2.4.1 Type of laboratory

A central laboratory (see laboratory manual for contact details) will be used for all protocol-mandated laboratory tests (with the exception of urine pregnancy tests), including re-tests due to laboratory abnormalities and laboratory tests performed at unscheduled visits.

Local laboratory results of the parameters described in Section 7.2.4.2 will only be collected in exceptional circumstances (e.g., hospitalization of the subject due to a medical emergency, and missing central laboratory results from a scheduled or unscheduled visit). The local laboratory results (with the corresponding normal ranges) must be recorded in the eCRF.

If two or more consecutive central laboratory samples are lost or cannot be analyzed for whatever reason, the investigator will collect an additional sample as soon as possible to repeat the analysis, unless a local laboratory sample was collected within the same time-window and these test results are available.

Laboratory reports will be provided by the central laboratory to the investigator/delegate. In the event of specific (pre-defined in the laboratory manual) laboratory abnormalities, the central laboratory will alert the sponsor and the site personnel.

All laboratory reports must be reviewed, signed and dated by the investigator/delegate within 10 working days of receipt and filed with the source documentation.

A re-test may be performed if the laboratory result is missing or to repeat an abnormal laboratory result. A re-test does not need to be reported as an unscheduled visit [see Section 7.1.2].

The investigator/delegate must indicate on the laboratory report whether abnormal values are considered clinically relevant or not. Clinically relevant laboratory findings that are known at the time of signing of the ICF must be recorded in the medical history or FD forms of the eCRF. Any clinically relevant laboratory abnormalities as per investigator judgment detected after signing of the ICF must be reported as an AE or SAE as appropriate [see Section 9], and must be followed until the value returns to within the normal range or is considered stable and no longer clinically relevant.

Details about the collection, sampling, storage, shipment procedures, and reporting of results and abnormal findings can be found in the laboratory manual.

7.2.4.2 Laboratory tests

Unless otherwise specified, the date of each laboratory sample will be collected in the eCRF.

7.2.4.2.1 Blood tests

Blood samples will be drawn under fasted^b condition (i.e., skipping breakfast) and when applicable before the morning administration of the study treatment at all scheduled and unscheduled visits.

Hematology:

- Hemoglobin (g/L);
- Hematocrit (%);
- Erythrocyte count (reticulocyte count) ($10^{12}/L$);
- Leukocyte count with differential counts ($10^9/L$);
- Platelet count ($10^9/L$).

Blood chemistry:

- ALT (U/L), AST (U/L), alkaline phosphatase (U/L);
- Total and direct bilirubin ($\mu\text{mol}/L$);
- Creatinine ($\mu\text{mol}/L$) measured using an enzymatic assay;
- eGFR* ($\text{mL}/\text{min}/1.73 \text{ m}^2$);
- Blood urea nitrogen (mmol/L);
- Uric acid ($\mu\text{mol}/L$);
- Albumin (g/L), protein total (g/L);
- Glucose (mmol/L), HbA1c (%);
- Cholesterol (mmol/L), triglycerides (mmol/L);
- Sodium, potassium, chloride, calcium (mmol/L);
- N-terminal pro-brain natriuretic peptide (ng/L).

*eGFR will be estimated using the CKD-EPI_{creatinine} equation [Levey 2009] as follows:

$$\text{eGFR}_{\text{creatinine}} = 141 \times \min(\text{Scr}/\kappa, 1)^\alpha \times \max(\text{Scr}/\kappa, 1)^{-1.209} \times 0.993^{\text{Age}} \times 1.018 \text{ (if female)} \times 1.159 \text{ (if black)}$$

where:

Scr = serum creatinine in mg/dL

$\kappa = 0.7$ for females, $\kappa = 0.9$ for males,

^b Subjects must not be requested to be in a fasted state (for the purpose of the study) at the screening visit unless the ICF has already been fully signed.

$\alpha = -0.329$ for females, $\alpha = -0.411$ for males,
min = the minimum of Scr / κ or 1, max = the maximum of Scr / κ or 1

Cardiac enzymes:

- High sensitivity troponin T ($\mu\text{g/L}$).

α -Galactosidase A:

An extra blood sample will be collected at the screening visit and randomization visit to assess the α -GalA in leukocytes (nmol/h/mg of protein). The samples will be shipped to the central laboratory for analysis.

7.2.4.2.2 Urinalysis

A midstream, clean-catch urine specimen will be collected for dipstick analysis and determination of creatinine ($\mu\text{mol/L}$), albumin (mg/L), UACR (mg/g) at all scheduled and unscheduled visits. The collected urine will be transferred into standard urine collection tube for shipment to central laboratory.

7.2.4.2.3 Pregnancy tests

A serum pregnancy test for women of childbearing potential will be performed at screening. A urine pregnancy test will be performed at randomization and monthly thereafter with locally approved kits provided by the site. If pregnancy is suspected during the study, a serum pregnancy test must be performed immediately.

The results of the urine pregnancy tests will not be collected in the eCRF. Serum pregnancy tests will be sent to the central lab for analysis and the result will be sent to the investigator/delegate (see laboratory manual for details on collection, sampling, storage, shipment procedures, and reporting of results).

Reporting procedures of pregnancy are described in Section [9.4.1](#).

7.2.4.2.4 Fecal analyses

A fecal sample will be collected at the screening visit in subjects who report diarrhea symptoms to assess subject eligibility (exclusion criteria #8b, see Section [4.4](#)).

If no stool is available on the day of the screening visit, the subject will be provided with collection material and instructed by the site personnel how to collect, store and ship a stool sample. The subject will record the date and time at which the sample was produced.

The collected fecal samples will be transferred by the study personnel as described in the laboratory manual and study specific laboratory flowchart.

Stool exam will include calprotectin test, fecal occult blood test, stool culture, and test for ova and parasites.

7.2.5 Quality of life assessments

7.2.5.1 36-Item Short Form Health Survey Version 2

The SF-36v2™ questionnaire (SF-36v2™ Health Survey© 1996, 2000 by Medical Outcomes Trust and Quality Metric Incorporated) is used to assess the subject's QoL. The SF-36v2™ will be completed by the subject at the randomization visit and Month 6 (Month 6 PTOP visit if subject is in the PTOP), using the eDiary [see Section 7.2.2.1].

In the SF-36v2™ questionnaire, subjects are instructed to rate their health and capacity to perform activities of daily living in 8 domains including physical functioning, physical role limitations and mental health during the last 4 weeks. Raw domain scores are determined and transformed to a 0–100 scale as described in the SF-36v2™ manual [Maruish 2011]. Individual domain scores are used to determine the physical and mental component summary scores as described in the SF-36v2™ manual [Maruish 2011].

A sample of the SF-36v2™ (in English) is provided in Appendix 6.

The sponsor has been granted a license agreement for the use of the SF-36v2™ questionnaire. The individual questionnaires will be completed only in countries for which validated translations are available.

7.2.6 Pharmacokinetic assessments

7.2.6.1 Pharmacokinetic assessments

Pre-dose blood samples for determination of PK will be collected for all subjects at the Month 1 visit and all subsequent visits to provide information about the study treatment exposure in the target population.

In addition, post-dose (0.5 h, 1 h, 1.5 h, 2 h, 2.5 h, 3 h, 3.5 h, 4 h, 6 h, 8 h, 10 h, and 12 h) blood samples will be collected at the Month 1 visit in a subset of 36 subjects to explore the 12 h PK profile of lucerastat and if necessary, to identify its potential metabolites.

7.2.6.2 Sampling, labeling, storage and shipment

The date and exact actual clock time of collection of each blood sample will be entered in the eCRF as well as the exact dates and time of the study treatment administration prior to and after blood draw.

Details about the collection, sampling, storage, and shipment procedures can be found in the laboratory manual.

7.2.6.3 Bioanalysis

The analysis of lucerastat and if needed, possible metabolites in plasma will be performed using a validated liquid chromatography coupled to tandem mass spectrometry assay. The foreseen limit of quantification of lucerastat is 50 ng/mL.

The analysis of lucerastat and, if needed, its possible metabolites in plasma will be performed by the Idorsia bioanalytical laboratory. To minimize the possibility of systematic unblinding, the values of the PK parameters will not be communicated to the investigator and study personnel, subjects, CRAs, and sponsor and vendor/CRO personnel involved in the conduct of the study until the study database is locked.

The samples will be destroyed upon signature of the CSR and if applicable, the metabolite profiling report.

7.2.7 Biomarker assessments

7.2.7.1 Biomarkers of Fabry disease and their metabolic precursors

Plasma and urinary samples for analysis of biomarkers of FD and their metabolic precursors will be collected at all scheduled visits (pre-dose). The date and exact actual clock time of collection of each blood sample and urine sample will be entered in the eCRF.

Gb3 and lysoGb3, along with the Gb3 metabolic precursors GlcCer and LacCer will be quantified in plasma. Gb3 and lysoGb3 will be quantified in urine and normalized to creatinine.

A central laboratory (see laboratory manual for contact details) will be used for all protocol-mandated biomarker assessments. To minimize the possibility for systematic unblinding, biomarker laboratory results will not be communicated to investigator and study personnel, the subjects, CRAs, and any sponsor personnel and vendor/CRO personnel involved in the conduct of the study until the study database is locked.

7.2.7.2 Other non-genetic research samples

Extra plasma, serum and urine samples will be collected at trough at the randomization visit, Month 6 visit or EOT visit for additional non-genetic analyses including analysis of biomarkers that characterize FD or FD treatment characteristics (e.g., measurement of levels of antibodies against ERT, other analysis may be added after study closure, if scientific rationale has become available through new research). Those samples may be stored in the sponsor's research biorepository for a maximum of 15 years. Study participants may request these samples be destroyed at any time.

No genetic analysis will be conducted.

Details about the collection, sampling, storage and shipment procedures can be found in the laboratory manual.

8 STUDY COMPLETION AND POST-STUDY TREATMENT / MEDICAL CARE

8.1 Study completion as per protocol

Subjects who complete the 6-month, double-blind study treatment period, and if applicable FU1 and FU2, are considered to have completed the study as per protocol.

8.2 Premature withdrawal from study

Subjects may voluntarily withdraw from the study without justification for any reason at any time. Subjects are considered withdrawn if they state an intention to withdraw further participation in all components of the study (i.e., withdrawal of consent), die, or are lost to follow-up. If a subject withdraws consent, no further data will be collected in the eCRF from the date of withdrawal onward. The investigator may withdraw a subject from the study (without regard to the subject's consent) if, on balance, he/she believes that continued participation in the study would be contrary to the best interests of the subject. Withdrawal from the study may also result from a decision by the sponsor for any reason, including premature termination or suspension of the study.

Subjects are considered as lost to follow-up if all repeated attempts by the investigator to communicate with the individual have failed. The site must take preventive measures to avoid a subject being lost to follow-up (e.g., document different ways of contact such as telephone number, home address, email address, person to be contacted if the subject cannot be reached). If the subject cannot be reached, the site must make reasonable repeated efforts to contact the subject, document all attempts (date, time and type of contact made), and enter the loss of follow-up information into the eCRF. The following methods must be used: at least 3 contacts (e.g., telephone calls, or e-mails) must be placed to the last available telephone number or e-mail address) and 1 registered letter must be sent by post to the last available home address. Additional methods may be acceptable if they are compliant with local rules/regulations (e.g., a visit by site personnel to the subject's home), respecting the subject's right to privacy. If the subject is still unreachable after all contact attempts listed above he/she will be considered to be lost to follow-up.

The reason for premature withdrawal from the study must be recorded in the eCRF.

If for whatever reason (except death or loss-to-follow-up) a subject is withdrawn from the study, the investigator should make best efforts to schedule a last appointment / telephone call to assess the safety and well-being of the subject, collect unused study treatment and discuss follow-up medical care. Data obtained during this last appointment / telephone call will be recorded in the subjects' medical records but it will not be collected in the eCRF.

The investigator must provide follow-up medical care for all subjects who are prematurely withdrawn from the study, or must refer them for appropriate ongoing care, as described in Section 8.4.

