9.3 Reporting procedures

9.3.1 Reporting of adverse events

All AEs with an onset date after signing of the ICF and up to 30 days after study treatment discontinuation or up to the last visit of the PTOP period (whichever is the latest) must be recorded on specific AE forms of the eCRF.

Information to be collected in an AE form in the eCRF includes date of onset, action taken with the study treatment, outcome of AE, date of resolution (if applicable) and PI's assessment of intensity, and relationship to study treatment, study design or protocol mandated procedures.

Information on worsening of intensity will be collected on a new AE form. If the AE lessens in intensity, no change in the severity is required to be reported.

Follow-up information on ongoing AE obtained after the subject's EOS visit will not be collected in the eCRF.

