#### **8.5 Study withdrawal**

Subjects who complete the 6-month, double-blind study treatment period, and, if applicable, FU1 and FU2, are considered to have completed the study as per protocol.

Study withdrawals are subjects having not completed the study (defined as subjects with “Did the subjects complete the study?” ticked “No” in the eCRF end of study status form).

Possible reasons for study withdrawal are as follows:

- Withdrawal by subject
- AE
- Lost to FU
- Death
- Other

In addition, the site has to indicate if the reason for study withdrawal is related to the COVID-19 pandemic.

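### Protocol 8.2 keeps AEs first learned at the last safety contact out of the eCRF even when consent was not withdrawn, which contradicts the AE recording rule in 9.3.1

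*Protocol*

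**What the plan says.** Protocol 8.2 contains two separate non-collection rules.

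- The first concerns consent: "If a subject withdraws consent, no further data will be collected in the eCRF from the date of withdrawal onward".
- The second concerns the last contact. It opens "If for whatever reason (except death or loss-to-follow-up) a subject is withdrawn from the study" and asks the investigator to try to arrange a final appointment or call, partly to assess safety. What is obtained goes into the subject's "medical records but it will not be collected in the eCRF".

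The same section provides routes out of the study that do not depend on consent. "The investigator may withdraw a subject from the study" when continued participation would be against that subject's best interests, whether or not the subject agrees. "Withdrawal from the study may also result from a decision by the sponsor for any reason", and early termination or suspension of the study counts among those reasons.

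Protocol 9.3.1 sets the recording rule. "All AEs with an onset date after signing of the ICF and up to 30 days after study treatment discontinuation", or up to the last PTOP visit if that is later, "must be recorded on specific AE forms of the eCRF". It makes no exception for withdrawn subjects. Section 9.3.2 sends SAEs in the same window to the sponsor's drug safety department on an SAE form.

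Protocol 3.1.1 applies the safety follow-up period to everyone who does not enter the open-label extension, and 7.1 includes AEs and SAEs in the FU1 call. SAP section 10 treats AEs with onset from the start of treatment to EOT + 30 days as treatment-emergent.

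**The concern.** A subject who has withdrawn consent to further data collection should have none collected, and the first rule in 8.2 ensures that. The second rule is not tied to consent. Where the investigator or the sponsor ends participation, the site may hold a contact meant to assess safety, learn of an AE within the reporting window, and then be told by 8.2 to keep it out of the eCRF and by 9.3.1 to enter it.

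The completeness of the AE tables is at stake, and safety and tolerability is a secondary objective. The protocol describes no route into the clinical database for a non-serious AE other than the eCRF AE form, so an event left off that form is not counted. An SAE would still reach the sponsor under 9.3.2, but it could then be in the safety database with no matching eCRF record. Sites could also resolve the conflict in different ways, so AE capture would depend on which section a site followed.

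**Working it through.** The plan gives no figure to reproduce. The check is a comparison of the rules by type of departure.

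| How the subject leaves | What 8.2 says about eCRF data | Does 9.3.1 still require AE entry? | Conflict? |
|---|---|---|---|
| Stops treatment only | Not covered: 5.1.9 says such a subject is not withdrawn, and PTOP follow-up applies | Yes, and AEs are collected at PTOP visits (Table 6) | No |
| Dies or is lost to follow-up | Excepted from the last-contact sentence | Yes, for AEs already known | No, as there is no last contact |
| Withdraws consent | Collection stops at withdrawal under the separate consent rule | Yes as worded, but the consent rule explains the limit | None of substance |
| Withdrawn by investigator or sponsor, consent intact | Last-contact data not collected | Yes, with no exception stated | **Yes** |

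**What the last-contact sentence adds.** In the third row the consent rule already ends collection, so the sentence changes nothing. Its independent effect falls on the fourth row, where no consent reason for leaving AEs out exists.

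**Whether such an AE would have been analysed.** SAP section 10 retains onsets up to EOT + 30 days. The last contact can take place inside that window, and an AE reported then may have begun before it. Such an AE qualifies as treatment-emergent under the SAP but would be absent from the data.

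**Whether FU1 closes the gap.** Under 3.1.1 and 7.1, FU1 covers everyone not entering the extension and collects AEs. Table 5 places it 30 to 37 days after the last dose. If FU1 is also held for a subject withdrawn by the investigator or sponsor, an AE kept out at the last contact could be recorded then. If the last contact takes the place of FU1, it could not. The documents do not say which applies.

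**Size.** The documents give no expected withdrawal rate, no split by who initiates withdrawal, and no AE rate in withdrawn subjects, so the loss cannot be calculated. Only the weight of one missed subject can be given, from the approximate arm sizes in SAP section 2:

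- lucerastat: 1/79 = 1.3%
- placebo: 1/39 = 2.6%

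These are the shifts in a single AE percentage, taking all randomized subjects as the denominator. They apply only if the subject is not already counted for that preferred term, because SAP 16.1 counts a subject once per term.

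**The case against.** The strongest reply is that this is a narrow wording conflict with little practical reach. Most of that reply is right:

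- The study-specific safety criteria in 5.1.10 stop study treatment and do not end study participation. A subject stopped for safety normally has an EOT visit and enters the PTOP with AE collection intact.
- AEs known before the last contact, including one that prompted the withdrawal, should already be in the eCRF. The reason for withdrawal must be recorded there too.
- SAEs reach the sponsor by their own route.
- FU1 nominally covers much of the same window.

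A reader might go further and infer that AEs are lost for every withdrawn subject, that the loss falls on those most likely to have AEs, or that it differs by arm and shifts AE percentages by several points. The documents support none of this. In the SAP 8.5 list introduced by "Possible reasons for study withdrawal are as follows", AE does appear, but the list does not say who initiated the withdrawal, and a subject may withdraw consent because of an AE. A shift of several points would need several subjects in one arm, each with the same AE, first learned at that contact and not already counted. Nothing in the plan allows that to be estimated.

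It could also be said that 9.3.1 itself excludes late information, since follow-up on ongoing AEs obtained after the EOS visit is not entered in the eCRF. That exclusion concerns follow-up of AEs already recorded. It does not cover new AEs with onset inside the reporting window, so it does not reconcile the two sections.

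**Conclusion.** The contradiction is real. For a subject withdrawn by the investigator or sponsor with consent intact, a site that first learns of an in-window AE at the last contact cannot follow both 8.2 and 9.3.1. If it follows 8.2, a non-serious AE is left out of the treatment-emergent tables, and an SAE may appear in one database only.

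The effect is limited to AEs first learned at that contact in these withdrawals, which are probably few, and FU1 may recover some of them. Its overall size cannot be stated. Direction and imbalance between arms are also unknown, so the point does not support a claim of biased safety results. There is one exception to the small scale: because 8.2 counts early termination of the study as a sponsor withdrawal, its literal wording would then reach every ongoing subject. Section 8.3 allows the sponsor to add procedures in that event but does not lift the bar.

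The conclusion rests on reading 8.2 as written and on the eCRF being the source of the AE tables. The correction is worth making because it costs almost nothing and decides which AEs are counted.

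**What to change.** Limit the non-collection sentence in Protocol 8.2 to subjects who have withdrawn consent. Add that, for withdrawal initiated by the investigator or the sponsor, AEs and SAEs learned at the last contact and falling within the windows of 9.3.1 and 9.3.2 are entered in the eCRF, and that SAEs also go on the SAE form. State in the same place whether FU1 is still held for these subjects, so that 8.2 agrees with 3.1.1 and 7.1.

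This takes one or two sentences of protocol text. Section 8.2 already asks for the contact and its documentation, so no new visit is needed, and the SAP's definition of treatment-emergent AEs is unchanged. The only cost is entering data the site already holds.
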